5.2.6.2.2 AE reporting to the sponsor and timelines

The investigator must report SAEs, AESIs, and non-serious AEs which are relevant for the reported SAE or AESI immediately to the sponsor’s unique entry point (within 24 hours of becoming aware of the event) (country specific contact details will be provided in the ISF). The same timeline applies if follow-up information becomes available. In specific occasions, the investigator could inform the sponsor upfront via telephone. This does not replace the requirement to complete and send the BI SAE form.

With receipt of any further information to these events, a follow-up SAE form has to be provided. For follow-up information the same rules and timeline apply as for initial information. All (S)AEs, including those persisting after individual patient’s end of trial must be followed up until they have resolved, have been assessed as “chronic” or “stable”, or no further information can be obtained.

5.2.6.2.3 Pregnancy

In rare cases, pregnancy might occur in a clinical trial. Once a patient has been enrolled in the clinical trial and has taken trial medication, the investigator must report any drug exposure during pregnancy in a trial participant immediately (within 24 hours) by means of Part A of the Pregnancy Monitoring Form to the sponsor’s unique entry point.

The outcome of the pregnancy associated with the drug exposure during pregnancy must be followed up and reported to the sponsor's unique entry point on the Pregnancy Monitoring Form for Clinical Studies (Part B). The ISF will contain the Pregnancy Monitoring Form for Clinical Studies (Part A and B).

As pregnancy itself is not to be reported as an AE, in the absence of an accompanying SAE and/or AESI, only the Pregnancy Monitoring Form for Clinical Studies and not the SAE form is to be completed. If there is an SAE and/or AESI associated with the pregnancy an SAE form must be completed in addition.

5.3 DRUG CONCENTRATION MEASUREMENTS AND PHARMACOKINETICS

5.3.1 Assessment of pharmacokinetics

Spesolimab concentrations will be reported descriptively. No PK parameters will be calculated. PK data will be incorporated into a larger pharmacometric analysis with other trials of the spesolimab project. Also, ADA and neutralizing antibody (Nab) will be measured and their impact on PK will be assessed. The relationship between PK and selected efficacy endpoints, biomarkers and AEs may be assessed. PK and demographic data together with treatment assignments and dosing information may be made available to individuals outside of the trial team for the purpose of PK dataset generation in accordance with sponsor's standard procedures.

5.3.2 Methods of sample collection

Plasma/Serum samples may be used for further methodological investigations (ex: for future stability testing). However, only data for measuring the analyte and antibody responses to the analyte will be generated by these investigations. After completion of the trial, the plasma/serum samples may be used for further methodological investigations, e.g. for stability testing. However, only data related to the analyte and data related to the ADAs will be generated by these additional investigations. The samples will be discarded after completion of the additional investigations but not later than █ years upon the final study report has been signed.

[figure not shown]
5.3.2.1 Plasma sampling for PK analysis

For quantification of spesolimab plasma concentrations, blood will be taken from a forearm vein into a K2EDTA (ethylenediaminetetraacetic acid) anticoagulant blood-drawing tube at the time points listed in the [Flow Chart](#) under plasma PK. Handling procedures can be found in the laboratory manual.

5.3.2.2 Sampling for ADA/Nab assessment

For ADA assessment, blood will be taken from a forearm vein into a K2EDTA anticoagulant blood-drawing tube at the time points listed in the [Flow Chart](#) under ADA/Nab. For Nab assessment, blood will be taken from a forearm vein into a serum blood-drawing tube at the

time points listed in the Flow Chart under ADA/Nab. Handling procedures can be found in the laboratory manual (see ISF).

5.4 ASSESSMENT OF BIOMARKER(S)

This section refers to exploratory biomarkers. Established biomarkers of efficacy and safety are described and discussed in [Sections 5.1](#) and [5.2](#).

5.4.1 Biochemical and cellular biomarkers

Serum will be collected as indicated in the [Flow Chart](#) to assess changes in protein levels of select IL36 pathway and disease related markers. The biomarker assay analysis of samples will be performed in a staged approach. The initial analysis will focus on selected time points and depending on these results a decision will be made about further analysis of all samples. This is due to the exploratory nature of the mechanism being tested and the timing of effect on candidate biomarkers in the study.

5.4.2 Pharmacogenomics biomarkers

Whole blood samples will be collected as indicated in [Flow Chart](#) and used for RNA extraction and subsequent gene expression analysis to identify genes involved in the drug's mechanism of action or the pathology of the disease. The biomarker analysis of samples will be performed in a staged approach. The initial analysis will focus on selected time points and depending on these results a decision will be made about further analysis of all samples. This is due to the exploratory nature of the mechanism being tested and the timing of effect on candidate biomarkers in the study.

5.4.3 Methods of sample collection

Detailed instructions on sampling, preparation, processing, shipment and storage are provided in the laboratory manual. For sampling timepoints refer to the [Flow Chart](#).

5.5 BIOBANKING

Not applicable.

5.6 OTHER ASSESSMENTS

5.6.1 Photographs

Subjects will have photographs taken of their disease response during the study. The photographs will be taken at designated study visits listed in the [Flow Chart](#). The cameras for the photographs will be standardized and supplied to the site by a central photography service. Sites will submit the digital images to the centralized photography service. Training and detailed instructions will be provided by the central photography vendor.

5.7 APPROPRIATENESS OF MEASUREMENTS

All methods used are standard methods.

6. INVESTIGATIONAL PLAN

6.1 VISIT SCHEDULE

All patients are to adhere to the visit schedule as specified in the [Flow Chart](#). Each visit date (with its window) up to the EoS Visit is to be counted from Visit 1 (visit with first IMP administration). If any of these visits has to be rescheduled, the date of the subsequent visit should be calculated again from Visit 1. Additional visits (unscheduled visits) for the purpose of re-testing of laboratory parameters or AE monitoring may be included as deemed necessary by the investigator. If a visit was missed due to any reason, the Clinical Trial Leader (CT Leader) must be contacted to discuss if the visit must be skipped.

For detailed description of the visit schedule and the trial procedures, please refer to the [Flow Chart](#) and its footnotes.

Details relating to study drug administration and treatment interruptions are provided in [Section 4.1.4](#).

Study measurements and assessments are scheduled to occur 'before' trial medication administration. For planned individual plasma concentration sampling times refer to the [Flow Chart](#). Sampling times will be recorded and used for PK analysis.

In exceptional cases, if standard visits at the trial sites are impossible because of COVID-19 related safety risks, the investigator must assess the risk-benefit for each individual patient and may decide to perform a visit remotely if this is in the best interests of the patient and if agreed with the sponsor. All COVID-19 related deviations from the original schedule of visits and procedures will be documented and the implications considered for the analysis of the trial data.

In the event of force majeure or other disruptive circumstances (e.g. pandemic, war) the investigational plan as per this CTP may not be feasible at a site. With the consent of the patient, sponsor and investigator may agree on alternative, back-up or rescue methodology which may include but will not be limited to virtual patient visits and assessments, home healthcare nurse visits, and direct-to-patient shipments of trial treatment. Such alternative measures may be described in a specific Crisis Management Manual as part of the initial submission package, and will also be mentioned in the patient information leaflet. The implementation of these measures will depend on patient's consent, operational feasibility, local law and regulations. If alternative methodology is implemented, the deviations from the original plan will be precisely documented.

6.2 DETAILS OF TRIAL PROCEDURES AT SELECTED VISITS

Study procedures to be performed at each visit are listed in the [Flow Chart](#) and respective CTP sections. Refer to [Section 5](#) for explanations of the specified assessments and procedural details.

Patient Reported outcomes (PROs) should be completed by the patient on his/her own in a quiet area/room before any other visit assessments or treatments and, as much as possible, before any interaction with the investigator or other members of the study team.

Separate from the PROs above, the evaluation of efficacy assessments are to be conducted preferably by the same qualified assessor, whenever possible, throughout the study.

PROs and assessments should preferably be done prior to any study drug administration.

6.2.1 Visit 1 – Start of Treatment

For the comprehensive list of the trial procedures required at Visit 1 please refer to the [Flow Chart](#). Study drug will start at Visit 1.

Visit 1 should preferably be performed in one visit combined with the EoT visit of the preceding 1368-0052 PoCC trial. Any duplicate procedures across the two studies are performed only once when the visit is combined. When these two visits across both studies do not occur on the same day then a modification of procedures will need to be considered. Refer to the [Flow Chart](#) for procedures that are identical across the two visits and for further information on any modification of procedures.

If a patient performs the EoT visit in the 1368-0052 PoCC study and a newly observed medical finding, for example, prohibits the patient to immediately enrol into this study, then the patient can come back for Visit 1 at a later date per the opinion of the investigator and after discussion with the sponsor. The maximum gap for enrolling into this trial is 2 weeks after the EoT in the 1368-0052 PoCC trial. During this gap, patients can take systemic and topical antibiotics for disease worsening as per the investigator discretion (see [Section 4.2](#)). However, biologics, immunomodulators and opioid analgesics are not allowed for HS and non-HS indications.

Refer to [Section 4.1.4](#) for study drug assignment and administration. Administration of the study drug is blinded at Visit 1 only.

6.2.1.1 Informed Consent

The patient must be given sufficient time to consider participation in this extension trial. Therefore, to facilitate the logistics of Visit 1 and the consenting process, information about this extension trial should be discussed with potentially eligible patients in advance of Visit 1 of this trial. A copy of the patient information and consent form of the extension trial should be provided to potentially eligible patients preferably no later than Visit 8 of the previous 1368-0052 PoCC trial. This will provide potential patients with sufficient time to consider their possible participation in this extension trial. At Visit 1, the investigator or delegate obtains written consent of the patient's own free will with the informed consent form after confirming that the patient understands the contents. Also refer to [Section 8.1](#).

Study requirements, including the procedure for the follow-up of prematurely withdrawn patients, must be fully explained to the patient and written informed consent obtained prior to initiating any study-related evaluations. The importance of staying in the trial until

completion of all study requirements should be emphasized. No trial procedures can be done unless the patient has consented to taking part in the trial.

Once consented, the patient is considered to be enrolled in the trial. Once informed consent is obtained, the IRT contact is to be performed by the site. IRT will assign a patient number at the time IRT registration. Collection of SAEs and AEs begins immediately after the patient has signed the consent form (please refer to [Section 5.2.6.2.1](#)). The patient should be recorded on the enrolment log.

6.2.1.2 Infection Testing

Infection testing will include TB, Hepatitis B, Hepatitis C, and HIV assessments (see [Table 5.2.3:1](#)). **The results of the Infection Testing will not be available until after the patient receives their first dose at Visit 1.** See [Section 3.3.4.1](#) for Discontinuation Rules.

Interferon Gamma Release Assay

Patients with indeterminate / suspected false-positive QuantiFERON TB or invalid/borderline T-spot test result may have the test repeated once. If after repeat testing the QuantiFERON TB result is “indeterminate”, a PPD skin test may be performed locally. A tuberculin skin test reaction $\geq 10\text{mm}$ ($\geq 5\text{mm}$ if receiving $\geq 15\text{mg/d}$ prednisone or its equivalent) is considered positive.

In patients with a previously (i.e., in the previous PoCC trial or in this ongoing extension trial) negative IGRA for TB the test should be repeated every 52 weeks, as long as the results are negative. Refer to [Table 5.2.3:1](#).

If latent tuberculosis is diagnosed during the trial, then patients can receive anti-tuberculosis treatment as per investigator discretion and continue receiving study medication as per investigator.

6.2.2 Treatment period(s)

The treatment period is from Visit 1 to the EoT Visit at Week [REDACTED]. For the comprehensive list of the trial procedures required during these visits please refer to the [Flow Chart](#) and its footnotes. See also [Section 5.2](#) for details of all safety assessments.

Refer to [Section 4.1.4](#) for study drug administration.

For information on the collection of photographs of skin lesions, please see [Section 5.6.1](#)

6.2.3 Follow-up period and trial completion

For the comprehensive list of the trial procedures required at the EoT, FUP 1, and the EoS visits please refer to [Flow Chart](#) and its footnotes.

The FUP 1 Visit occurs 2 weeks after the EoT Visit; this is 2 weeks after the patient has received their last dose of trial medication.

The EoS visit will take place at the end of the REP which is 16 weeks after last injection of trial medication. Please also refer to the REP in [Section 1.2.3](#). After conclusion of trial the patients will be treated according to the standard of care.

Patients who discontinue trial treatment prematurely should undergo the EoT visit as soon as possible, the FUP 1 Visit two weeks after the last dose, and the EoS Visit 16 weeks after the last dose. If a patient discontinues the study during a scheduled treatment visit then the visit is considered an EoT visit.

In the event a patient discontinues treatment and the trial prematurely and is unable to perform both FUP 1 and EoS visits, (only willing or physically can only perform one visit) then the early FUP 1 Visit procedures should be followed.

For all patients, trial completion status must be recorded on the corresponding eCRFs.

Treatment completion is defined as a patient completing the EoT Visit after receiving approximately 2 years of treatment without early discontinuation of study treatment.

Trial completion is defined as a patient having reached the EoS Visit within the specified window per protocol.

If needed in the opinion of the investigator, after the EoS visit additional visits may be scheduled for continued safety monitoring.

Abnormal assessments or lab values judged clinically relevant by the investigator will be monitored until they are returned to a medically acceptable level.

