1.2.3 Residual Effect Period

The Residual Effect Period (REP) of spesolimab is 16 weeks. This is the period after the last dose with measurable drug levels and/or PD effects still likely to be present.

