2.1.2 Primary endpoint(s)

The primary endpoint is the occurrence of treatment emergent adverse events (TEAE) up to the end of maintenance treatment period including REP (i.e., 16 weeks after the last study treatment).

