After the baseline visit the assessment ‘since last visit’ will be performed at each clinic or phone visit (‘since last visit’ version). The investigator is to review positive and negative reports for plausibility and clinical relevance. Doubtful reports may be repeated or reports may be validated by a consulting psychiatrist. If there is a confirmed positive report of suicidal behaviour or suicidal ideation type 4 or 5 after start of trial, the investigator is to immediately interview the subject during the clinic visit, and/or is to consult a psychiatrist. If

the positive report is confirmed, appropriate actions for the subject's safety have to be initiated.

All C-SSRS reports of suicidal ideation type 4 or 5 and all reports of suicidal behaviour must be reported as SAEs by the investigator. For 'Self-injurious behaviour, no suicidal intent' (Type 11) standard AE / SAE reporting rules are to be applied. For each negative report (suicidal ideation type 1, 2 or 3) after start of the trial, the investigator is to decide based on clinical judgment whether it represents an AE as defined in the CTP, and if it is considered an AE then it must be reported accordingly.

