7. STATISTICAL METHODS AND DETERMINATION OF SAMPLE SIZE

The primary objective of this trial is to assess the long-term safety of spesolimab in patients with HS who have completed the 1368-0052 PoCC trial and are qualified for entry into this trial. The secondary objectives are to evaluate efficacy at a lower dose than tested in PoCC trial.

For primary analysis of the primary endpoint, all adverse events with an onset between start of treatment and end of the REP (i.e., 16 weeks after the last study treatment) will be included.

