7.3 HANDLING OF MISSING DATA

Every effort will be made to collect complete data at all visits. However, missing data will still occur and approaches to handle this are proposed below.

For the safety data, including the primary endpoint, no missing data imputations are planned.

For secondary binary efficacy endpoints, a NRI approach will be applied to the missing visits; that is, imputing as a failure to achieve a response in the visits with missing endpoint score, however:

- If there are visits with available data both before and after the visit with a missing outcome, then impute as a success only if both the preceding and the following measurement indicate success and no rescue medication has been given during this period.
- Otherwise, impute as a failure to achieve a response (i.e. no response imputation).

For secondary continuous efficacy endpoints, MMRM method may be applied to handle the missing data.

Further analyses to assess the robustness of the results on efficacy endpoint will be described in the TSAP if necessary.

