6. GENERAL ANALYSIS DEFINITIONS

6.1 TREATMENT(S)

For basic study information on the treatment to be administered, assignment to treatment, and selection of dose, cf. Section 4 of the CTP.

The study phases are defined relative to first dose at Day 1 as below:

Table 6.1: 1 Flow chart of analysis phases of the study

Study analysis phase	Description	Start (included)	End (included)
Screening phase	Screening	Earliest of (Date of informed consent, first screening procedure)	Date/time of start of the first study dose minus 1 second.
Treatment phase & Residual effects period	On-treatment period	Date/time of start of the first study dose regardless of infusion or injection (Day 1)	Earliest of: i) Date of last study drug regardless of infusion or injection + 112 days at 23:59, ii) cut-off for interim analysis if applicable.
Follow-up phase ¹ (if applicable)	Off-treatment period (if applicable)	Date of end of last study dose + 113 days at 0:00 a.m.	Latest of: i) Date of EOS visit; ii) last contact date on trial termination page at 11:59 p.m.

Dates are defined individually per patient. If more than one date is associated with a specific visit, measurements associated with a specific date are assigned to a study analysis phase according to the rules specified in the table. An analysis phase will not extend beyond the start date of the following phase.

¹ The off-treatment period (i.e. Follow-up phase) only exists if the date of EoS visit or the last contact date is after the date of end of last administration + 112 days.

Treatments will be labelled for final analysis as follows:

Tables will be displayed also by prior treatment from parent trial for final analysis:

- “Prior Placebo” (applicable to analysis for whole on-treatment period, i.e., including infusion loading at Day 1 for placebo patients from parent trial]
 - “Prior Placebo + uptitration at Week [] (applicable to analysis for whole on-treatment period, i.e., including infusion loading at Day 1 for placebo patients from parent trial and after dose escalation]
 - “Prior Placebo + Other” (applicable to analysis for whole on-treatment period, i.e., placebo patients from parent trial who received [] dose [] during all [] period or who were early discontinued before Week [])

- “Prior Speso” (applicable to analysis for whole on-treatment period, i.e., including [REDACTED] at Day 1 for speso patients from parent trial, before and post dose escalation)

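### Patients who leave the trial early and can make only one more visit have no planned adverse event contact at week 16, although the primary TEAE window runs to day 112 after the last dose

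*Protocol*

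**What the plan says.** **The window.** Protocol 2.1.2 defines the primary endpoint as occurrence of TEAEs "up to the end of maintenance treatment period including REP (i.e., 16 weeks after the last study treatment"). Section 7 repeats this for the primary analysis: "all adverse events with an onset between start of treatment and end of the REP (i.e., 16 weeks after the last study treatment) will be" counted. Section 1.2.3 gives the reason for the length: "The Residual Effect Period (REP) of spesolimab is 16 weeks". SAP Table 6.1: 1 ends the on-treatment period at "Date of last study drug regardless of infusion or injection + 112 days at 23:59", or at an interim cut-off if earlier.

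**The visits.** The default after early discontinuation is EoT, FUP 1 two weeks after the last dose and EoS 16 weeks after it (Protocol Flow Chart from W14, 3.3.4 and 6.2.3). Section 3.3.4 wants the same visits proposed even to patients who withdraw consent. Section 6.2.3 then makes one exception. Where a patient has left both treatment and the trial and is "only willing or physically can only perform one visit) then the early FUP 1 Visit procedures should be followed". Of FUP 1 it says: "this is 2 weeks after the patient has received their last dose of trial medication".

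**Collection and counting.** New adverse events are actively collected from consent to the EoS visit (Protocol 5.2.6.2.1). Section 7.3 states: "For the safety data, including the primary endpoint, no missing data imputations are planned". SAP section 7 bases percentages on every patient in the set, whether or not values are missing. Exposure-adjusted rates censor event-free patients at the last contact date if that comes first (Protocol 7.2.5, SAP 7.8.1).

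**The SAP visit tables.** SAP Tables 6.7: 1 to 6.7: 3 have a row for patients who stop treatment early and will not follow the full schedule. The only visit in that row is an EOS at last dose plus 112 days.

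**The concern.** The exception offers a visit built for week 2 to a patient whose primary-endpoint window stays open until week 16. If that visit is the last contact, nobody is scheduled to ask about new events in the remaining weeks. These are weeks in which the protocol itself expects measurable drug or pharmacodynamic effect. In the crude tables the patient then counts as event-free for whatever was not seen.

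What is at stake is the count of late-onset SAEs, AESIs and individual preferred terms. With about 45 patients, one patient is 1/45 = 2.2 percentage points. Section 3.3.4.1 lists reasons for stopping that include adverse events, suicidality, certain infections and persistent non-response. The pool from which one-visit leavers come is therefore not a random sample, and the loss could be informative.

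**Working it through.** **1. The plan's own window.** 16 weeks × 7 = 112 days. This reproduces the 112 days in SAP Table 6.1: 1.

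**2. Days without planned ascertainment, if the single visit is held at FUP 1 time.** Inputs are FUP 1 at day 14 with a window of ±3 days (Flow Chart).
- Day 14: 112 − 14 = 98 days, or 14.0 weeks; 98/112 = 87.5%
- Day 11: 112 − 11 = 101 days, 90.2%
- Day 17: 112 − 17 = 95 days, 84.8%

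A single visit at day 112 that asks about events since the last visit would leave 0 days.

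**3. Share of the patient's whole TEAE window.** 14 / (week of last dose + 16):
- Week 12: 14/28 = 50%
- Week 24: 14/40 = 35%
- Week 52: 14/68 = 21%

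**4. Scale across the trial.** The documents give no dropout rate and no one-visit rate, so this is an assumed range, not an estimate. Let f be the fraction of 45 patients who take the one-visit exit, from 5% to 30%.
- Patients: 45f = 2.25 to 13.5
- Time lost: 45f × 98/365.25 = 0.6 to 3.6 patient-years
- Share of all planned post-dose time: f × 98/112 = 4.4% to 26%
- Share of all planned time: 14 × 45f / (45 × 120 weeks) = 0.6% to 3.5%, assuming 104 weeks of treatment plus 16

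**5. Patients missing from a crude count.** Assume a constant first-event rate r and no earlier event of that type in the one-visit leavers. The chance of a first event in the unseen time is p = 1 − exp(−r × 98/365.25). The shortfall in the crude percentage is f × p.

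| Assumed r per 100 patient-years | p | Patients missed, f = 5% to 30% | Percentage points |
|---|---|---|---|
| 5 | 1.3% | 0.03 to 0.18 | 0.1 to 0.4 |
| 20 | 5.2% | 0.12 to 0.71 | 0.3 to 1.6 |
| 100 | 23.5% | 0.53 to 3.18 | 1.2 to 7.1 |

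At high rates most patients will already have had the event before leaving, so the last row overstates the shortfall. For the same reason the percentage with any TEAE hardly moves.

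**6. Protocol against SAP.** For nearly the same group, Protocol 6.2.3 prescribes FUP 1 procedures while the SAP tables list only an EOS at day 112. SAP 6.7 says adverse events are not assigned through visit windows, so the mismatch does not change how a reported event is counted. It does leave open which final contact is expected.

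**The case against.** The strongest case against is that this is a narrow exception inside a sound schedule.

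- **Scope.** A reader might infer that early leavers in general lose 14 of the 16 weeks. The documents do not support that. Patients who only stop treatment stay in the trial (3.3.4.1), and the default for every early leaver includes the 16-week visit. This objection stands in full.
- **Procedures, not a date.** Section 6.2.3 names a set of procedures. FUP 1 covers the EoS safety items and adds a complete physical examination, questionnaires and lesion counts, so choosing it for an only visit is reasonable. This also stands: the 98 days are conditional on the visit being held at FUP 1 time. But an undated visit does not secure the window either.
- **Later contact is not forbidden.** True; the text is silent, so it would be wrong to say that later contact is excluded. Events already reported are followed past the patient's end of trial (5.2.6.2.2), but that does not find new ones. The C-SSRS section says its assessment "will be performed at each clinic or phone visit", and section 6.1 allows remote visits for COVID-19 or force majeure. Neither provision is written for this patient.
- **The SAP has a day-112 row.** It does, but an analysis table assigns data to visits. It does not schedule them.
- **Rates already censor.** Correct. The exposure-adjusted rate leaves out the unseen time and is affected only if leaving is informative. The crude frequency tables have no such adjustment.
- **Disposition is reported.** SAP section 7 tabulates trial completion and withdrawals by reason. That is close to the count wanted, but it does not say who lacks adverse event follow-up to day 112.

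**Conclusion.** The gap is real but confined to patients who stop both treatment and the trial and can make only one of the two remaining visits. For each of them, if the visit falls at the FUP 1 time point, 98 of 112 days (95 to 101) have no planned ascertainment of new events while the patient remains in the crude denominator.

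The consequence is limited to crude SAE, AESI and single-term percentages. Its size cannot be derived from the documents. Under the assumed one-visit fractions of 5% to 30% and event rates of 5 to 20 per 100 patient-years, it is about 0.1 to 1.6 percentage points, so probably small. A reader might go further and conclude that the primary endpoint as a whole is materially biased low. The documents do not support that: the proportion with any TEAE barely moves, the exposure-adjusted rates censor at last contact, and nothing shows how many one-visit leavers there will be or that they differ from other leavers.

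The change is worth making because it is cheap, improves detection of late serious events, and removes a mismatch between protocol and SAP.

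**What to change.** 1. **Protocol 6.2.3.** State when the single site visit takes place. Add that, when only one site visit is possible, AEs, SAEs, AESIs and concomitant therapy are also collected by telephone 16 weeks after the last dose, within the EoS window, from patients who have not refused contact. Record that date as the last contact date, so that the exposure-adjusted rates use it.
2. **SAP Tables 6.7: 1 to 6.7: 3.** Reconcile the row for early discontinuers (EOS at last dose plus 112 days) with the amended 6.2.3.
3. **SAP 7.8.1.** Beside the primary endpoint, report the number of SAF patients without adverse event follow-up to day 112.

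The cost is one call per affected patient, a short protocol amendment and one extra table line. Reported adverse event percentages may rise slightly. The call will not reach patients who refuse all contact, so the count in step 3 is needed in any case.
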